
5.0 Study Procedures

Shoulder impingement is a syndrome characterized by shoulder pain that is exacerbated by passive and/or active elevation, with positive provocative testing for impingement such as Neer and Hawkins tests, and/or the diagnosis of subacromial bursitis based on tenderness to palpation of the acromion. Generally, patients who present with shoulder impingement will be treated initially with non-invasive measures such as activity modification, ice, physical therapy, and a trial of oral NSAIDs. If those measures do not provide adequate relief, then patients will be offered a therapeutic subacromial injection. The investigators will follow these principles of conservative management except when the patients' pain is

severely limiting their activities of daily living and their ability to work and provide for themselves or when patients are having pain at night that interferes with sleep. In those situations, a subacromial injection may be offered prior to attempting less invasive measures. Ultimately, the decision to offer a subacromial injection will be made in clinic by the investigators based on their clinical judgment. All of the investigators are fellowship-trained orthopedic surgeons who subspecialize in shoulder diseases. Their decision to offer patients a subacromial injection will be independent of whether the patients wish to participate in the study. Patients will be given the opportunity to participate in the study only after the decision to offer an injection is made by the clinician. Patients will not be solicited outside of a regularly scheduled clinic visit to participate in this study.

Investigational Drug Service (IDS) staff will not be directly involved with the handling of the study drugs; however, a plan has been documented and agreed upon by both parties regarding study drug supply, storage, randomization, preparation, administration, and accountability (Study Drug Management Form). Therefore, the clinic staff will maintain the blinding of the surgeons, who are licensed by the medical board of Texas to perform the injection.

[figure not shown]
[figure not shown]
Drugs that will be injected will be dispensed to medically-licensed research personnel by the clinic staff to be delivered to the treating surgeon. For the methylprednisolone treatment arm, the injection will consist of 9 mL of lidocaine HCl (1% without epinephrine) and 1 mL of methylprednisolone acetate (80 mg/mL). For the ketorolac treatment arm, the injection will consist of 8 mL of lidocaine HCl (1% without epinephrine) and 2 mL of injectable ketorolac tromethamine (30 mg/mL). The total injection volume in each treatment arm will be 10 mL. After the clinic encounter, a blinded member of the research staff will call or email the patient to complete the ASES questionnaire at 2, 4, and 12 weeks post-injection. If the follow-up could not be performed exactly at 2, 4, or 12 weeks post-injection, investigators will allow examination and measurements at ± 3 days.

6.0 Study Product Description

The following information has all been retrieved from the methylprednisolone acetate and the ketorolac tromethamine package inserts.

[figure not shown]
Formulation, Packaging, and Labeling

Ketorolac tromethamine is a member of the NSAIDs. The chemical name for the drug is: (\pm) -5-benzoyl2,3-dihydro-1H-pyrrolizine-1-carboxylic acid, compound with 2-amino-2-(hydroxymethyl)-1,3-propanediol (1:1). Its structural formula is presented below.

Ketorolac tromethamine is a racemic mixture of [-]S and [+]R ketorolac tromethamine. It is soluble in water. Injectable ketorolac tromethamine is available for intravenous (IV) administration as 15 mg in 1 mL and 30 mg in 1 mL in sterile solution. For intramuscular (IM) administration, ketorolac tromethamine is available only as 60 mg in 2 mL (30 mg/mL) in sterile solution. In this case, the latter contains 10% alcohol and 8.70 mg of sodium chloride in sterile water. The pH range is 6.9 to 7.9 and is adjusted with sodium hydroxide and/or hydrochloric acid. The sterile solutions are clear and slightly yellow in color.

Injectable methylprednisolone acetate is an anti-inflammatory glucocorticoid. The chemical name for the drug is: pregn-1,4-diene-3,20-dione, 21-(acetoxy)-11,17-dihydroxy-6-methyl-,(6 α ,11 β)-. Its structural formula is presented below.

Injectable methylprednisolone acetate is used for intramuscular, intra-articular, soft-tissue or intralesional injection. It is available in three strengths: 20 mg/mL, 40 mg/mL, and 80 mg/mL. In this study, the latter (80 mg/mL) will be used as indicated for large joints in the FDA brochure of this medication. Each mL of this preparation contains 80 mg of methylprednisolone acetate, 28.2 mg of polyethylene glycol 3350, 1.88 mg of polysorbate 80, 6.59 mg of monobasic sodium phosphate, 1.37 mg of dibasic sodium phosphate, and 8.88 mg of benzyl alcohol (as a preservative). The pH range is 3.5 to 7.0 and is adjusted with sodium hydroxide and/or hydrochloric acid.

Product Storage and Stability

Injectable ketorolac tromethamine must be stored between 15°C (59°F) and 30°C (86°F). Injectable methylprednisolone acetate must be stored between 20°C (68°F) and 25°C (77°F). They both should be kept at controlled room temperature while being protected from light.

Dosage, Preparation and Administration of Study Intervention/Investigational Product

The sealed envelopes that contain each patient's therapeutic arm assignment will be equally distributed to the study staff prior to the enrollment. They will be kept in locked containers in each investigator's clinic. Only study staff will have access to the envelopes. After patient enrollment and informed consent completion, the study staff will open one of the sequentially numbered envelopes and the patient assigned the corresponding subject number written on the outside of the envelope. The study staff will prepare the appropriate injection (see below) for the assigned treatment arm. The syringe will be covered with opaque tape prior to being given to the surgeon for administration. The injection will take place in a private clinic room in compliance with HIPAA guidelines. The surgeon will administer the injection into the subacromial space using standard bony landmarks from the posterolateral approach. After the injection is given by the research MD, the clinic staff will then dispose of the syringe without disclosing the treatment arm assignment to the patient nor the provider. Patients' subject number will be recorded on their consent form and in their electronic medical record. The statistician will unlock the master list only after patient enrollment and follow-up are complete, or if mandated by any regulatory bodies. Blinding will also be uncovered in case of a patient developing an adverse event while being followed in the trial.

Both drugs will be intra-articularly delivered through a single subacromial injection within 30 to 45 minutes. For the methylprednisolone treatment arm, the injection will consist of 9 mL of lidocaine HCl (1% without epinephrine) and 1 mL of methylprednisolone acetate (80 mg/mL). For the ketorolac treatment arm, the injection will consist of 8 mL of lidocaine HCl (1% without epinephrine) and 2 mL of injectable ketorolac tromethamine (30 mg/mL). The total injection volume in each treatment arm will be 10 mL. These drugs are not suitable for multi-dose use. Following administration of the desired dose, any remaining suspension will be returned to IDS.

Modification of Study Intervention/Investigational Product for a Participant

The study consists of a subacromial single dose injection of either methylprednisolone acetate (80 mg) or ketorolac tromethamine (60 mg). Patients will then be followed-up for 12 weeks and ASES data will be recorded at 2, 4, and 12 weeks post-injection. If the follow-up could not be performed exactly at 2, 4, or 12 weeks post-injection, investigators will allow examination and measurements at ± 3 days. No additional injections will be needed, and therefore, no dose modification will be required. Patients meeting any of the exclusion criteria will not be initially enrolled in the study.

Accountability Procedures for the Study Intervention/Investigational Product(s)

Drugs that will be injected will be prepared by clinic staff and will then be delivered to the treating surgeon. The clinic staff will be responsible of maintaining the drug accountability at each enrollment site. There will be an inventory accountability log kept by the clinic staff at each location. For the methylprednisolone treatment arm, the injection will consist

of 9 mL of lidocaine HCl (1% without epinephrine) and 1 mL of methylprednisolone acetate (80 mg/mL). For the ketorolac treatment arm, the injection will consist of 8 mL of lidocaine HCl (1% without epinephrine) and 2 mL of injectable ketorolac tromethamine (30 mg/mL). The total injection volume in each treatment arm will be 10 mL. Treatment will be administered once and patients will be evaluated afterwards at 2, 4, and 12 weeks post-injection. Injectable drugs administered in this study are not suitable for multi-dose use.

Assessment of Subject Compliance with Study Intervention/Investigational Product

The responsible investigator will administer the treatment in a double-blinded fashion to the patient, who will be examined and followed at 2, 4, and 12 weeks by the same investigator. At enrollment and at 12 weeks, the follow-ups will be performed in the clinic, whereas at 2 and 4 weeks, this will be performed by phone contact/email. The ASES questionnaire will be completed prior to the injection, and then at those time points (2, 4, and 12 weeks). If the follow-up could not be performed exactly at 2, 4, or 12 weeks post-injection, investigators will allow examination and measurements at ± 3 days.

Risks

The risks associated with this study include the risks of randomization, loss of confidentiality, and the burden associated with answering a questionnaire. Also, administration of methylprednisolone or ketorolac into the subacromial space is associated with certain risks; however, eligible subjects of this study would receive one of these medications regardless of their participation in this research. The ASES questionnaire at follow up will take approximately four minutes to fill out at each of the three follow-up time points (2, 4, and 12 weeks post-injection). The risk of loss of confidentiality will be minimized by storing all protected health information in locked filing cabinets in the orthopedic offices of UTMB, accessible only to those study staff that have a need to access. All digital health information will be de-identified with research-specific subject numbers and it will be stored on password protected and encrypted computers on the secure institution's network. Only serious and unanticipated problems associated with the injectable product will be reported to the IRB.

Minor side effects of steroid injections include post-injection flare, uterine bleeding, and facial erythema; major toxicities include Cushing syndrome and radiologic deterioration of joints and osteonecrosis [12, 17]. Local adverse effect of steroid injection includes permanent skin depigmentation, infection, tendon rupture, and fat necrosis or calcification. Systemic side effects of ketorolac include increased risk for cardiovascular thrombotic events including myocardial infarction and stroke, GI bleeding, ulceration and perforation, renal failure, and risk of bleeding.

Benefits

There are no foreseeable benefits to the subjects for participation in this study. If ketorolac is shown to be equivalent or superior to methylprednisolone, then the potential benefits to

the society are multiple. These include health care cost savings, standardization of care, and the furthering of orthopedic knowledge.

Concomitant Medications/Treatments

The information below report mainly drug interactions with other medications on the package insert of the agent of interest. This also included the current literature pertaining to each medication. In either arm, the drug is delivered intra-articularly (locally), which mitigates its systemic absorption and therefore its potential side effects.

Modern evidence do not indicate a significant interaction between ketorolac tromethamine and warfarin, heparin, aspirin, digoxin, diuretics, probenecid, lithium, methotrexate, ACE inhibitors, and angiotensin II receptor antagonists. Sporadic cases of epilepsy and hallucinations have been reported when combining ketorolac with antiepileptic or psychoactive drugs, respectively. When administered with SSRI, an increased risk of bleeding was noted. However, all of these adverse events occurred with IV (systemic) rather than intra-articular (local) administration of the drug. No teratogenicity or tumorigenicity were reported to date.

Recent evidence indicates an interaction between corticosteroids and either antifungals or antibiotics. However, patients with any sign or symptom of infection will be screened, and therefore excluded, prior to the injection in case an infection is suspected. Corticosteroids have been shown to interact with anticoagulants. Nonetheless, bleeding problems are also screened for prior to the injection, and if present, patients will be excluded from the trial. Corticosteroids may also intervene with hepatic enzyme inducers/inhibitors, and patients with liver diseases will be excluded. No adequate studies have been conducted to evaluate the tumorigenic effect of corticosteroids. These agents may exhibit teratogenic effects, which is the reason why pregnant women will be take part of the study.

7.0 Adverse Events or Unanticipated Problems involving Risk to Participants or Others

Most of these contra-indications are retrieved from the medications package inserts. Due to the randomization and blinding design of the study, a contra-indication to either drug (methylprednisolone acetate or ketorolac tromethamine) is considered an absolute contra-indication for the patient to be enrolled in the study. Subjects meeting any of these conditions at baseline will be excluded from study participation. These conditions include: allergy/intolerance to steroids or NSAIDs symptoms less than one month, pregnancy or breastfeeding, pre-existing asthma, psychiatric illness, previous shoulder injection within the past three months, evidence of other confounding shoulder pathology on plain radiographs such as calcific tendonitis, MRI evidence or history of rotator cuff tear, active comorbidities of the ipsilateral extremity such as lateral epicondylitis and cervical radiculopathy, moderate to severe glenohumeral arthritis, systemic inflammatory conditions, kidney or liver disease, gastrointestinal (GI) ulcers, bleeding disorders, pending litigation or work-related claims related to the shoulder, previous shoulder surgery on the

affected shoulder, evidence of local infection, evidence of adhesive capsulitis, evidence of shoulder instability, and bilateral shoulder pain.

The International Council for Harmonisation of Technical Requirements for Pharmaceuticals for Human Use (ICH) defines an adverse event (AE) as any untoward medical occurrence in a patient or clinical investigation subject administered a pharmaceutical product regardless of its causal relationship to the study treatment. An AE can therefore be any unfavorable and unintended sign, symptom, or disease temporally associated with the use of medicinal product. The occurrence of an AE may come to the attention of study personnel during study visits and interviews of a study recipient presenting for medical care, or upon review by a study monitor.

All AEs including local and systemic reactions not meeting the criteria for “serious adverse events” should be captured on the appropriate case report form. Information to be collected includes event description, time of onset, clinician’s assessment of severity, relationship to study product (assessed only by those with the training and authority to make a diagnosis, which would include MD, PA, Nurse Practitioner, DO, or DDS), and time of resolution/stabilization of the event. All AEs occurring while on study must be documented appropriately regardless of relationship. All AEs will be followed to adequate resolution.

Any medical condition that is present at the time that the patient is screened should be considered as baseline and not reported as an AE. However, if it deteriorates at any time during the study, it should be recorded as an AE.

All AEs must be graded for severity and relationship to study product. In such cases, the statistician will uncovering the patient blinding and randomization process to reveal the medication that was administered to the patient.

Severity of Event

All AEs will be assessed by the clinician using a protocol defined grading system. For events not included in the protocol defined grading system, than the following guidelines will be used to quantify intensity.

Mild – Events require minimal or no treatment and do not interfere with the patient’s daily activities; **Moderate** – Events result in a low level of inconvenience or concern with the therapeutic measures; **Moderate** – Events may cause some interference with functioning; **Severe** – Events interrupt a patient’s usual daily activity and may require systemic drug therapy or other treatment. Severe events are usually incapacitating; and **Life threatening** – Any adverse drug experience that places the patient or subject, in the view of the investigator, at immediate risk of death from the reaction as it occurred, i.e., it does not include a reaction that had it occurred in a more severe form, might have caused death.

Changes in the severity of an AE should be documented to allow an assessment of the duration of the event at each level of intensity to be performed. Adverse events characterized as intermittent require documentation of onset and duration of each episode.

Relationship to Study Products

The clinician's assessment of an AE's relationship to test article is part of the documentation process, but it is not a factor in determining what is or is not reported in the study. If there is any doubt as to whether a clinical observation is an AE, the event should be reported. All AEs must have their relationship to study product assessed using the terms: associated or not associated. In a clinical trial, the study product must always be suspect. To help assess, the following guidelines are used: **Associated** – Event temporally related to the administration of the study product and no other etiology explains the event; and **Not Associated** – Event temporally independent of study product and/or the event appears to be explained by another etiology.

Serious Adverse Event (SAE)

An SAE is defined as an AE that meets one of the following conditions: (1) Death during the period of protocol defined surveillance; (2) Life threatening event (defined as a subject at immediate risk of death at the time of the event); (3) An event requiring inpatient hospitalization or prolongation of existing hospitalization during the period of protocol defined surveillance, results in congenital anomaly or birth defect, results in a persistent or significant disability/incapacity; or (4) Any other important medical event that may not result in death, be life threatening, or require hospitalization, may be considered a serious adverse experience when, based upon appropriate medical judgment, the event may jeopardize the subject and may require medical or surgical intervention to prevent one of the outcomes listed above.

All SAEs will be recorded on the appropriate SAE case report form, followed through resolution by a study clinician, and reviewed and evaluated by a study clinician.

Reporting Procedures for Serious Adverse Events

Any AE considered serious by the principal investigator or co-investigators or which meets the aforementioned criteria must be submitted on the SAE form to the IRB in accordance with IRB policies and procedures.

In addition, SAE's should be de-identified and anonymously reported to all investigators to emphasize on the possibility of other patients exhibiting a similar problem. The investigators are responsible of transmitting this information to their respective IRBs, who will then report the events that are serious, unexpected, and associated with the study product(s) to the Food and Drug Administration (FDA) within the required timelines as specified in 21 CFR Part 312.32: fatal and life-threatening events within 7 calendar days (by phone or fax) and all other SAEs in writing within 15 calendar days. All serious events designed as "not associated" to study product(s), will be reported to the FDA at least annually in a summary format.

The study clinician will complete a sponsor provided Serious Adverse Event Form within the following timelines: (1) All deaths and immediately life-threatening events, whether Protocol – Version 2 – November 13, 2018

related or unrelated, will be recorded on the Serious Adverse Event Form and sent by fax within 24 hours of site awareness; and (2) Serious adverse events other than death and immediately life-threatening events, regardless of relationship, will be reported via fax by the site within 72 hours of becoming aware of the event.

All SAEs will be followed until satisfactory resolution or until the principal investigator or co-investigator deems the event to be chronic or the patient to be stable.

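### No structured adverse event questioning is specified at weeks 2, 4 or 12, so minor and transient harms are likely to be under-recorded and any safety comparison is descriptive only

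*Combined protocol and SAP*

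**What the plan says.** **Scheduled contacts.** Section 5.0 states that "a blinded member of the research staff will call or email the patient to complete the ASES questionnaire at 2, 4, and 12 weeks post-injection". No other content is described. The Risks text in Section 6.0 puts the follow-up burden at about four minutes per time point, all of it for the ASES.

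**Mode of contact.** The subject compliance text in Section 6.0 describes a patient "who will be examined and followed at 2, 4, and 12 weeks by the same investigator". It then says "At enrollment and at 12 weeks, the follow-ups will be performed in the clinic". For the other two contacts it says "whereas at 2 and 4 weeks, this will be performed by phone contact/email". Week 12 is thus a clinic visit in Section 6.0 and a call or email in Section 5.0.

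**Detection of AEs.** Section 7.0 says "The occurrence of an AE may come to the attention of study personnel during study visits and interviews of a study recipient presenting for medical" …. The last route that it names is "or upon review by a study monitor".

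**Duty to record.** Section 7.0 also says "All AEs occurring while on study must be documented appropriately regardless of relationship". Onset, severity and its changes, relationship, resolution and each episode of an intermittent event are to be captured.

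**Named harms.** The Risks text lists minor steroid effects (flare, uterine bleeding, facial erythema), as well as local and major ones. The ketorolac list is mainly serious: cardiovascular events, gastrointestinal bleeding and perforation, renal failure.

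**Unblinding.** Section 4.0 and the administration text of Section 6.0 uncover the blind when a patient has an AE. Section 7.0 has the statistician reveal the drug when AEs are graded.

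**Analysis.** Section 9.0 plans ASES summaries by arm and no AE analysis.

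**The concern.** The plan sets a demanding recording duty without a procedure to feed it. The ASES, which Section 9.0 describes as measuring pain and function, cannot reveal facial erythema or bleeding. A patient who completes an emailed form at week 2 need not be asked anything else under the text as written.

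Timing adds to the gap. The first contact falls on day 11 to 17 (14 ± 3 days), by which time a flare may have passed. On the Section 6.0 reading the first clinic visit after injection is at week 12. On the Section 5.0 reading no visit is scheduled at all.

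At stake is how the safety counts will be read. In a trial that asks whether ketorolac can stand in for steroid, a low or equal count could be taken as reassurance when it partly reflects what was not asked. The loss could also differ by arm: the steroid list holds more minor events that may never prompt care, while the ketorolac list is mostly events that would.

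**Working it through.** **1. The plan's own figure.** The only computed size is for the ASES: 4 × (1.64 + 0.84)² × 12.3² / 12² = 25.85, rounded to 26; 26/0.8 = 32.5, rounded to 33; planned enrollment 40, or 20 per arm (Section 9.0). It reproduces, and nothing below changes it. No safety figure is stated.

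**2. Inputs.** n = 20 per arm comes from Section 9.0. True event rate p and capture fraction c (the share of events that get recorded) are assumptions, because the documents give neither.

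**3. What zero recorded events would exclude.** The chance of none recorded is (1 − cp)ⁿ. Setting this to 0.05 gives a one-sided 95% upper bound p = [1 − 0.05^(1/20)] / c = 0.139 / c.

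**4. Chance of recording none when p = 20% (assumed).** (1 − 0.2c)²⁰.

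| Capture c | Upper bound after 0/20 | P(none recorded), p = 20% |
|---|---|---|
| 1 | 13.9% | 0.80²⁰ = 1.2% |
| 0.5 | 27.8% | 0.90²⁰ = 12% |
| 0.25 | 55.6% | 0.95²⁰ = 36% |

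For an assumed 10% rate, expected recorded cases per arm are 20 × 0.10 × c = 2.0, 1.5 and 1.0 at c = 1, 0.75 and 0.5. The chance of at least one is 88%, 79% and 64%.

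**5. Would full capture allow a formal comparison?** Power of the two-sided Fisher exact test at 0.05, 20 per arm, with assumed true rates and equal capture in both arms:

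| True rates | c = 1 | c = 0.75 | c = 0.5 |
|---|---|---|---|
| 5% vs 20% | 17% | 9% | 3% |
| 5% vs 30% | 45% | 28% | 11% |

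The smallest significant split against zero is 5 vs 0 (p = 0.047); 4 vs 0 gives p = 0.106. By the usual two-proportion formula, 80% power needs about 76 per arm for 5% vs 20% and 36 per arm for 5% vs 30%. Better capture improves the counts but does not make the comparison confirmatory.

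**The case against.** A reader might infer that AEs are found only by chance, that harms will certainly be under-counted, and that the arms therefore cannot be compared on safety. The documents do not support this.

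- Section 7.0 names study visits and monitor review as well as patients seeking care, and Section 6.0 places a clinic follow-up at week 12. Doubtful events are to be reported, and withdrawn subjects remain in follow-up (Section 8.0).
- The AE case report form is not in the documents and may carry prompts. What can be said is that questioning is not specified, not that it will not happen.
- The same capture method applies to both blinded arms. The main limits on comparison are 20 patients per arm and the absence of an AE analysis in Section 9.0.
- A reader might also infer that the termination rule in Section 8.0 fails. For an assumed 20% rate, the chance of five or more recorded events in 20 falls from 37% at full capture to 4% at half. But the rule counts similar serious events, which are more likely to present for care and have 24- and 72-hour reporting limits in Section 7.0.
- The steroid tissue effects cited in Section 1.0 are adhesions and cartilage necrosis in rabbits. A questionnaire would not detect them.
- Eliciting more AEs has a cost: under the present unblinding text it would unblind more patients before a self-reported primary outcome.

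All of this stands, and it limits the point to non-serious events. It does not close the gap. The recording rules apply once an event is known. No monitoring procedure is described, and record review cannot find an event that nobody recorded. A single visit at week 12 is late for the onset and duration of a transient event.

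**Conclusion.** The point holds in limited form. No structured AE solicitation is specified at any scheduled contact, so non-serious and transient harms named in the protocol are likely to be under-recorded or recalled late, despite the duty to document all AEs. This is a judgement from the described procedures; the documents give nothing from which a capture rate could be computed.

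The figures for incomplete capture, such as the rise in the zero-event bound from 13.9% to 27.8% at half capture, are illustrations under assumed rates. The 13.9% itself depends only on n = 20. Any safety comparison at this size is descriptive with or without better capture, which makes the completeness of the counts the main thing the plan can improve. The sample size and the ASES analysis are unaffected. This is a cheap improvement rather than a flaw in the primary result.

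**What to change.** 1. In Section 5.0, the compliance text of Section 6.0, and Section 7.0, add one short AE question set to the existing week 2, 4 and 12 contacts, as a phone script and an email form. Include an open question and a prompt for each harm in the Risks text, with onset and end dates. Use identical wording in both arms, have blinded staff ask it, and pass positive answers to a study clinician for grading. State in Section 7.0 that AEs are elicited as well as spontaneously reported.
2. In Section 9.0, add AE counts by arm with exact confidence intervals, labelled descriptive.
3. Reconcile Sections 5.0 and 6.0 on the mode of the week 12 contact.
4. Before adopting item 1, reconcile the AE unblinding text in Sections 4.0, 6.0 and 7.0 with it, so that eliciting and grading a minor AE does not by itself unblind patients or assessors before the week 12 ASES.

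**Cost.** A few minutes per contact, one added form, more AE forms to complete and one added table; no new visit, staff or patients. If item 4 is skipped, the cost is also more unblinding ahead of the primary outcome.
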